6.8. Analysis Populations

The following analysis populations will be used in the statistical analysis. Analysis population membership will be determined prior to unblinding.

Intent-to-Treat (ITT) Population: The ITT population will consist of all randomized patients who received at least 1 dose of study treatment, with treatment assignment designated according to randomized treatment. This will be the primary population for the analysis of efficacy endpoints.

Per Protocol (PP) Population: The PP population will consist of the subset of the ITT population, excluding those patients who have had a major protocol violation. Major protocol violations will include all violations that would significantly impact assessment of safety and efficacy of the compound and will be finalized in advance of data lock and primary analyses. Violation of any of the following three inclusion criteria related to UC specific disease activity would exclude a patient from the PP population:

- Must have a confirmed diagnosis of UC by endoscopic and histologic evidence
- Must have a baseline Mayo score of 6-12 inclusive with endoscopic subscore of >=2
- Must have a baseline endoscopy with >= 15 cm involvement

Poor study drug compliance will also exclude the patient from the PP population. Poor study drug compliance is defined as taking less than 80% or more than 120% of study treatment during the entire treatment period.

The patients excluded from the PP population will be fully defined and documented with reasons for exclusion prior to database lock.

Safety Population: The Safety population will consist of all patients receiving any study treatment. All patients in the Safety population will be analyzed according to the highest dose of RPC1063 actually received and not according to the treatment they are randomized to receive, in the event there is a discrepancy.

6.9. **DMC**

An independent DMC will be charged with monitoring accumulating data from the trial, as well as general aspects of trial conduct.

The committee will meet periodically, approximately four times a year during the study, to review unblinded aggregate analyses by treatment group concerning enrollment, treatment compliance, adherence to follow-up schedule, and safety data from the trial. The DMC may recommend modifying or stopping the trial early due to safety concerns based on data reviews. The DMC will also review the Primary Endpoint (Week 8 Induction) and make recommendations taking into account both the efficacy results and the safety profile.

The blinding plan to assure that all personnel at Receptos and all personnel involved in the conduct of the study remain blinded to the results of reviews will be specified in the DMC Charter.

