13.5. Analysis Populations

The following analysis populations will be used in the statistical analysis:

Intent-to-Treat (ITT): The ITT population will consist of all randomized patients. The primary efficacy analysis will be carried out in the intent-to-treat population, with treatment assignment designated according to randomized treatment.

Modified Intent-to-Treat (MITT): The MITT population will consist of all randomized patients who received at least 1 dose of investigational drug, with treatment assignment designated according to randomized treatment.

Per Protocol (PP): The PP population will consist of the subset of the ITT population, excluding those patients who have had a major protocol violation. These will be defined prospectively, in advance of data lock and primary analyses, in the final SAP, by the (aggregate results blinded) project statistician.

PK: The PK population will consist of patients who have at least one baseline and one post-baseline PK assessment.

Safety: The Safety population will consist of all patients receiving any investigational drug and safety analyses will be carried out on this population according to treatment actually received.

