13.8.2. Primary Efficacy Analysis

The primary efficacy analysis will be completed based on the ITT population for the IP. The primary analysis will be carried out when all patients have completed (or would have been eligible to complete) the IP of the study.

The primary endpoint of clinical remission at Week 8 will be analyzed using the Cochran-Mantel-Haenszel (CMH) test, stratified by prior anti-TNF therapy experience. The primary analysis will use the data from the 1 mg dose and placebo groups and compare the remission rates in these 2 groups using a two-sided test at the $\alpha=0.05$ level of significance.

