6.16. Dosing Compliance

6.17. Treatment Compliance

6.18. Prior and Concomitant Medications

6.19. Efficacy Analyses

Analysis of all efficacy endpoints will primarily be based on the ITT population with treatment failure rules applied. Patients will be considered to have failed treatment if they have protocol-prohibited changes in concomitant UC medications, including an increase in corticosteroid dose from baseline to treat UC or a prolonged course of systemic corticosteroids >7 days for treatment of disease other than UC; initiation of an immune suppressing therapy including 6-MP or azathioprine or anti-TNF agents; a colectomy (partial or total) or an ostomy; or have discontinued study agent for lack of therapeutic effect before the week 8 evaluations. Patients with a treatment failure will be considered not to have achieved the dichotomous end points; and for continuous end points, their last values will be carried forward for all

visits subsequent to the time of treatment failure. Treatment failure rules will supersede other data handling rules.

The efficacy endpoints will also be analyzed in the PP population.

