8. DEVIATIONS FROM PROTOCOL

The analyses of the following endpoints specified in the protocol are not performed due to collected samples have not been analyzed at the time of database lock.

- Proportion of patients with histologic Remission at Week 8 for exploratory objectives and exploratory efficacy endpoints.
- Plasma protein biomarkers (cytokines, chemokines, other inflammatory proteins) as PD endpoint.

STATISTICAL ANALYSIS PLAN - OPEN LABEL PERIOD ADDENDUM

Title: A Phase 2, multi-center, randomized, double-blind, placebo-

controlled parallel-group study to evaluate the clinical efficacy and

safety of induction therapy with RPC1063 in patients with

moderately to severely active ulcerative colitis

Protocol: RPC01-202

Sponsor: Celgene International II Sàrl (see appended signature page)

[name] [name]

[contact]

Date: October 15, 2019

Status: Addendum to Version 2.0

CONFIDENTIAL

This document is a confidential communication of Receptos. Acceptance of this document constitutes agreement by the recipient that no unpublished information contained herein shall be published or disclosed without prior written approval, except that this document may be disclosed to the appropriate Institutional Review Board(s)/Independent Ethics

Committee(s) under the condition that they keep it confidential.

TABLE OF CONTENTS

SIGNA	ATURES	2
TABLE	E OF CONTENTS	3
LIST O	OF ABBREVIATIONS	4
1.	Introduction	5
2.	Study Design	5
3.	Analysis Cohorts	5
4.	DMC	5
5.	Patient Disposition	5
6.	OLP Baseline	5
7.	Efficacy Analyses	6
7.1.	Endpoints	6
7.2.	Mayo Score at the End of OLP	6
7.3.	Visit Windows	7
8.	Safety Analyses	8
9.	Guideline on Missing Date Imputation	8

LIST OF ABBREVIATIONS

AE adverse event DEF definition

DMC data monitoring committee

IP Induction Period ITT intent-to-treat

[figure not shown]
MP Maintenance Period

NRI Non-responder imputation
OLP Open-Label Treatment Period

SAE serious adverse event SAP statistical analysis plan

UC ulcerative colitis

1. Introduction

Study Design

3. Analysis Cohorts

- Intent-to-Treat (ITT) Analysis Cohorts will be labeled by randomized treatment in the parent study for all subjects who received at least one dose of RPC1063 1mg in OLP.
- Safety Analysis Cohorts will be labeled by actually received treatment in the parent study for all subjects who received east one dose of RPC1063 1mg in OLP.

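### The SAP applies the ITT label to dosed patients only, so the primary analysis runs on the protocol's MITT set and the protocol's ITT analysis appears nowhere

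*SAP*

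**What the plan says.** **Protocol.** Section 13.5 states: "The ITT population will consist of all randomized patients". It adds: "The primary efficacy analysis will be carried out in the intent-to-treat population, with treatment assignment designated according to randomized treatment". Section 13.8.2 repeats the commitment: "The primary efficacy analysis will be completed based on the ITT population for the IP". Section 13.5 also defines a second, narrower set: "The MITT population will consist of all randomized patients who received at least 1 dose of investigational drug", again analysed as randomized. Section 13.11 counts patients without data at the time point as nonresponders for the primary and the key secondary proportion endpoints.

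**SAP.** Section 6.8 states: "The ITT population will consist of all randomized patients who received at least 1 dose of study treatment", analysed as randomized, and continues: "This will be the primary population for the analysis of efficacy endpoints". Section 6.19 carries this forward: "Analysis of all efficacy endpoints will primarily be based on the ITT population with treatment failure rules applied". Section 6.19.5 places the missing-data sensitivity analyses in the same set, and the per-protocol set is a subset of it. MITT appears in the SAP's abbreviation list but is not defined in 6.8. Section 8, which lists departures from the protocol, opens with "The analyses of the following endpoints specified in the protocol are not performed" and names only histologic remission and plasma protein biomarkers.

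**The concern.** The protocol had both sets available and chose the all-randomized one for its primary test. The SAP reverses that choice under the same label and does not say so.

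Three things follow. The primary test is not run on the population to which the protocol commits. Patients can be excluded after randomization, and since each excluded patient would have counted as a nonresponder, the observed rate rises in whichever arm loses them (unless that rate is zero). And a study report that follows the SAP would call a dosed-only result ITT, which a reader holding the protocol would take to mean all randomized patients.

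**Working it through.** **1. The definitions side by side**

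| Set | Randomized | At least one dose required | Analysed as | Role |
|---|---|---|---|---|
| Protocol ITT (13.5) | yes | no | randomized | primary efficacy |
| Protocol MITT (13.5) | yes | yes | randomized | none assigned in 13.5 |
| SAP ITT (6.8) | yes | yes | randomized | primary efficacy |

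The SAP's ITT matches the protocol's MITT in every respect except that one says study treatment and the other investigational drug. Because 6.19, 6.19.5 and the per-protocol set all build on it, the SAP specifies no efficacy analysis of all randomized patients. The point stands on this comparison alone; the rest gives its size.

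**2. The plan's own sample-size figure**

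Inputs from Protocol 13.2: 60 per group, placebo 10%, active 31%, two-sided 0.05, 80% power. Pooled normal approximation:

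power = Φ{ (|p2 − p1| − 1.96·√[p̄(1−p̄)(1/n1 + 1/n2)]) / √[p1(1−p1)/n1 + p2(1−p2)/n2] }

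For 10% and 31%: (0.21 − 1.96 × 0.0737) / 0.0712 = 0.921, so power is 82.1%. A 20-point difference gives 78.9%, and exactly 80% is reached at 20.3 points. The stated 21 points is therefore the smallest whole-point difference with at least 80% power, and the figure reproduces.

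**3. Effect on the difference and on power**

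The documents state no number of undosed patients, so k is an assumption, from 0 to 3 per arm of 60. Remission among dosed patients is taken as 10% and 31%. In the all-randomized set an arm's rate is p × (60 − k)/60; in the dosed-only set it is p with n = 60 − k.

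| Undosed patients | Difference, all randomized | Difference, dosed only | Power, all randomized | Power, dosed only |
|---|---|---|---|---|
| none | 21.0 | 21.0 | 82.1% | 82.1% |
| 1 in each arm | 20.7 | 21.0 | 81.3% | 81.5% |
| 3 in each arm | 20.0 | 21.0 | 79.6% | 80.1% |
| 1, in 1 mg only | 20.5 | 21.0 | 80.5% | 81.9% |
| 3, all in 1 mg | 19.5 | 21.0 | 77.0% | 81.3% |
| 3, all in placebo | 21.5 | 21.0 | 84.3% | 81.0% |

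Example, three undosed in 1 mg: 0.31 × 57/60 − 0.10 = 0.1945, against 0.21.

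For an observed count of 19 remitters, the arm's rate is 19/60 = 31.7%, 19/59 = 32.2% with one undosed patient removed, 19/57 = 33.3% with three and 19/55 = 34.5% with five.

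**4. Effect on a borderline result**

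Uncorrected, unstratified chi-square, 1 mg against placebo:

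| Remitters | p |
|---|---|
| 14/60 vs 6/60 (all randomized) | 0.0500 (0.05004, not below 0.05) |
| 14/59 vs 6/60 | 0.0452 |
| 14/57 vs 6/60 | 0.0365 |
| 14/60 vs 6/59 | 0.055 |
| 14/60 vs 6/57 | 0.066 |
| 14/59 vs 6/59 | 0.0497 |

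The planned test is a CMH test stratified by prior anti-TNF therapy (SAP 6.19.2). Assume two equal strata of 30 per arm, since the documents anticipate about 50% with prior exposure, and remitters split evenly: 7/30 against 3/30 in each. Per stratum, the expected 1 mg count is 30 × 10/60 = 5 and the variance is 30·30·10·50/(60²·59) = 2.119. The statistic is (7 − 5 + 7 − 5)²/(2 × 2.119) = 3.776, p=0.052. Removing one undosed 1 mg patient from one stratum makes its expected count 29 × 10/59 = 4.915 and its variance 29·30·10·49/(59²·58) = 2.111. The statistic becomes 4.085²/4.230 = 3.944, p=0.047. The result crosses p<0.05, which is also the gate to the confirmatory secondary tests (SAP 6.19.3).

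**The case against.** The strongest reply is that this hardly matters in practice. Randomization follows verified eligibility, and the first dose is given in clinic at the same Day 1 visit (Protocol 9.11 and Table 1), so few or no randomized patients should go undosed. If all are dosed, the two sets coincide. Capsules are identical, nothing suggests that non-dosing depends on arm, and SAP 6.8 fixes population membership before unblinding. Losses on placebo raise p, as the table shows, so no systematic bias toward the drug is established. The flip needs a result on the boundary: 13/60 against 6/60 gives p=0.080 and stays at 0.060 with three 1 mg patients removed, 15/60 is already at 0.031, and 19/60 gives about 0.004. Undosed patients also remain visible in disposition, because SAP 6.11 tabulates the number randomized.

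All of that stands, and it limits the size. It does not restore the population that the protocol names, or correct the label.

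A second reply is that the SAP body may follow an earlier protocol version: it still describes 30-day follow-up (Section 4) and Day 5 cardiac monitoring (6.20.4), and the introductory text that might name the governing version is missing from the public copy. So it cannot be confirmed that Section 8 was incomplete when written. But nothing in the documents shows a version with a different ITT definition, and the October 2019 open-label addendum leaves 6.8 unchanged. The mismatch between the current documents remains.

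**Conclusion.** The SAP is wrong as written. Its ITT is the protocol's MITT, the substitution is not declared, and the protocol's primary analysis is specified nowhere in the SAP.

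The expected numerical effect is small. With an assumed 0 to 3 undosed patients per arm, the difference is overstated by 0 to 1.0 point if they are balanced and by up to 1.5 points if all are in the 1 mg arm; it is understated by up to 0.5 point if all are on placebo. Power differs by at most 0.6 points in the balanced case and by about 4 points when all are in the 1 mg arm. These figures rest on the plan's 10% and 31% rates and on an undosed count that the documents do not give. The borderline p-values show that one patient can decide the primary test; they do not forecast that this will happen, nor in which direction.

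**What to change.** In SAP 6.8, define ITT as all randomized patients, analysed as randomized, and state that undosed patients count as nonresponders for the proportion endpoints, in line with Protocol 13.11. Add the dosed set under the protocol's name, MITT, and repeat the primary analysis in it as a sensitivity analysis.

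If the sponsor prefers the dosed set as primary, the minimum is to call it MITT, declare and justify the change in SAP Section 8, and add an all-randomized analysis of the primary endpoint.

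The cost is SAP wording and one additional run of the primary analysis. No data collection changes. Remission rates may come out slightly lower in any arm with undosed patients.

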6.10. Final Analyses and Reporting

The primary analysis will be carried out when all patients have completed (or would have been eligible to complete) the IP of the study. The randomized treatment groups will be unblinded for both the IP and MP for the primary analysis. At the time of the primary analysis, the database will be locked for all visits through Week 8 and the available Mayo score data will be cleaned for all visits beyond Week 8. Data will continue to accrue for the MP and OLP visits. For this primary analysis, the safety analyses will be summarized for the IP only.

Final database lock will occur when all patients have completed the study and all data during the assessment periods has been monitored. In addition, no database may be locked, randomization code unblinded, or analyses completed (other than analyses for the DMC) until this SAP has been approved. All analyses outlined in the protocol and in this SAP (other than analyses conducted for the DMC) will be carried out after:

- The SAP has been approved
- All analysis populations are determined

Further exploratory analyses not necessarily identified in this SAP may be performed to support the CSR. Any post-hoc or unplanned analyses performed and not identified in this SAP will be clearly identified in the CSR.

6.11. Patient Disposition

The number and percentage of patients who signed the informed consent form, who were randomized, in each analysis population, who completed the study, who completed the IP, MP, and OLP will be summarized by treatment group. The number and percentage of patients who withdrew from the study and their reasons for withdrawal in each period will be tabulated by treatment group. All percentages will be based on the number of subjects in the ITT population. Disposition data will also be presented in a listing.

6.12. Demographics and Baseline Characteristics

The demographics and baseline characteristics will be presented in a table. The demographic characteristics consist of age, age category, sex, race, ethnicity, weight, height, body mass index (BMI), smoking history, and stratification factors. Age, weight, height, BMI, years as a smoker, and numbers of cigarettes, cigars, and pipes smoked per week will be summarized using the descriptive statistics. The number and percentage of patients in each age category (18-29, 30-39, 40-49, 50-59, 60-69, and 70-75, and < median, ≥ median) and in each race category (White, Black, Asian, American Indian or Alaska Native, Native Hawaiian or Other Pacific Islander, and Other) will be reported. The number and percentage of patients who have ever smoked, are current smokers, and who smoke each type of tobacco product will be reported. The summaries will be presented for the ITT population. Listings will be provided for demographic and baseline characteristic data.

6.13. General Medical History

Medical history information will be collected at the Screening Visit and on Day 1 (Visit 1).

Medical history will be summarized for the ITT population and will display the number and percentages of subjects with a significant history for each body system. Significant medical history included specific details will also be listed

6.14. Ulcerative Colitis Disease History

The following UC disease history parameters will be summarized using descriptive statistics:

- Age at UC diagnosis
- Years since UC diagnosis
- Mayo score at Baseline (using the central endoscopy score)
- Mayo score subgroup proportions using the central endoscopy score ($< 8 \text{ vs.} \ge 8$)
- Mayo score at Baseline (using the investigator endoscopy score)
- Mayo component scores at Baseline (stool frequency, rectal bleeding, physician's global assessment, investigator endoscopy score, central endoscopy score)
- Extent of disease (limited to left side of colon or extensive).

For partial UC diagnosis dates, the following imputation methods will be applied:

- If month and year are present but day is missing, then the day will be set to the 15th
- If year is present but not month and day, month and day will be set to July 1st
- If either imputation above results is a date >= the date of informed consent, then impute the date as informed consent date 1.

UC disease history will also be listed.

6.15. Protocol Deviations

Deviations and violations from the protocol will be recorded appropriately. If a patient was allowed to continue in the study, this will be recorded. According to the recommendations in the ICH guidelines, the protocol deviations will be classified into, but not necessarily limited to, the following categories:

- Inclusion/exclusion criteria deviation
- Prohibited medication use
- Incorrect treatment or dose
- Treatment non-compliance
- Procedure non-compliance
- Safety observation

Classification of deviations as major protocol violations, and decisions regarding exclusion of patients and/or patient data from the statistical analyses, will be decided on a case-by-case basis without knowledge of the treatment assigned and before database lock by the project statistician with input from the clinical study team. All protocol deviations will be presented in a summary table by protocol deviation category and treatment. Major protocol violations will be summarized separately. A listing of protocol deviations will also be presented that identifies those patients excluded from analyses.

[figure not shown]
6.16. Dosing Compliance

6.17. Treatment Compliance

6.18. Prior and Concomitant Medications

6.19. Efficacy Analyses

Analysis of all efficacy endpoints will primarily be based on the ITT population with treatment failure rules applied. Patients will be considered to have failed treatment if they have protocol-prohibited changes in concomitant UC medications, including an increase in corticosteroid dose from baseline to treat UC or a prolonged course of systemic corticosteroids >7 days for treatment of disease other than UC; initiation of an immune suppressing therapy including 6-MP or azathioprine or anti-TNF agents; a colectomy (partial or total) or an ostomy; or have discontinued study agent for lack of therapeutic effect before the week 8 evaluations. Patients with a treatment failure will be considered not to have achieved the dichotomous end points; and for continuous end points, their last values will be carried forward for all

visits subsequent to the time of treatment failure. Treatment failure rules will supersede other data handling rules.

The efficacy endpoints will also be analyzed in the PP population.

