13.11. Missing Data

For the primary analysis, as well as for the analyses of all key secondary efficacy endpoints that are defined as proportions, patients who do not provide data at the specified time point will be classified as nonresponders.

The Mayo score used for clinical endpoints in the study will utilize the Mayo endoscopy score derived from the central reader. In the case that a central endoscopic result is missing and the endoscopic subscore read by the Investigator will be utilized.

One of the key secondary efficacy endpoints (change in Mayo score) is a quantitative endpoint. For the key secondary analyses of this variable, missing values will be replaced by the least favorable observed change observed in the placebo group.

Sensitivity analyses of the primary and key secondary endpoints will be carried out to investigate the impact of missing data on the efficacy conclusions. These will include analyses of completed cases, observed cases, and multiple imputation model-based methods.

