4. STUDY DESIGN

Study RPC01-202 is a Phase 2, multi-center, randomized, double-blind, placebo-controlled, parallel-group study in patients with moderately to severely active UC.

This study includes 3 periods (Screening, Induction, and Maintenance) and an optional Open-Label Treatment Period (OLP). Following the 5-week Screening Period, eligible patients will be randomized and enter the 8-week placebo-controlled Induction Period (IP). Patients who are responders at Week 8 will continue on their assigned treatment in the 24-week Maintenance Period (MP). Non-responders at Week 8 have the option to enter the OLP. Patients who complete the MP will be given the option to participate in the OLP. Patients that enter the MP and experience disease relapse will also have the option to enter the OLP.

The study will include both patients that have received anti-TNF therapy and those that have not. It is anticipated that approximately 50% of the patients included in the study will have received anti-TNF therapy.

The study design is shown in Figure 1.

Induction Period (IP)

The 8-week IP will serve as a dose-finding study to assess the efficacy and safety of RPC1063 for the induction of clinical response, remission, and mucosal healing in patients with moderately to severely active UC. The IP will actually last for 9 weeks and consists of dose titration over 8 days followed by the full dose for 8-weeks.

Approximately 180 patients will be randomized in a 1:1:1 ratio to receive 1 of 3 treatment regimens:

- RPC1063 0.5 mg oral capsule daily
- RPC1063 1.0 mg oral capsule daily
- Placebo oral capsule daily

The randomization will be stratified by prior anti-TNF therapy experience (yes or no).

For patients randomized to one of the active treatment groups, there will be an 8 day dose titration regimen in the IP consisting of 4 days of treatment with RPC1063 0.25 mg, followed by 3 days treatment with RPC1063 0.5 mg, followed by the assigned treatment level for approximately 8 weeks.

Maintenance Period (MP)

All patients who complete the IP and are responders at Week 8 of the IP will enter the 24-week MP. Patients will continue to receive the same study treatment in the MP as received during the IP, and individual patient treatment will remain blinded until all patients have reached Week 32. The last visit in

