6.19.6. Other Efficacy Analyses

6.19.6.1. Mayo Score at Week **32**

The analyses will be performed for all available Week32 data at the time of database lock as described in Section 6.10.

- Proportion of patients in clinical remission at Week 32
- Proportion of patients in clinical response at Week 32
- Change in Mayo score from baseline at Week 32
- Proportion of patients with mucosal healing at Week 32

The endpoints that are defined as proportions will be analyzed using the same type of methodology as described for the primary analysis. Analyses of all proportion endpoints using the CMH test will be completed using the data from the two groups being compared. Quantitative secondary endpoints such as change in Mayo score will be analyzed using ANCOVA models with effects for treatment group and prior anti-TNF therapy experience, and with the baseline value of the corresponding endpoint included as a covariate. All analyses will be carried out using two-sided test at the 5% level of significance.

Actual and change from baseline in partial Mayo scores over time will be plotted.

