6.19.6.3. Partial Mayo Score

Partial Mayo score at all visits will be analyzed as follows:

- Proportion of subjects in clinical remission based on the partial Mayo score at each visit through last available
- Proportion of subjects in clinical response based on the partial Mayo score at each visit through last available
- Change in partial Mayo score from baseline at each visit through last available

The endpoints that are defined as proportions will be analyzed using the same type of methodology as described for the primary analysis. Analyses of all proportion endpoints using the CMH test will be

completed using the data from the two groups being compared. Quantitative secondary endpoints such as change in Mayo score will be analyzed using ANCOVA models with effects for treatment group and prior anti-TNF therapy experience, and with the baseline value of the corresponding endpoint included as a covariate. All analyses will be carried out using two-sided test at the 5% level of significance.

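### For continuous endpoints SAP 6.19 carries a treatment failure's last value forward, so a patient who fails in maintenance can be scored at Week 32 with a Week 8 responder's gain

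*SAP*

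**What the plan says.** SAP 6.19 (Efficacy Analyses) applies treatment-failure rules to every efficacy endpoint in the ITT population. The events listed are:

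- prohibited changes in UC medication, "including an increase in corticosteroid dose from baseline to treat UC";
- a long systemic steroid course for another disease;
- starting an immunosuppressant or anti-TNF agent;
- colectomy or ostomy;
- stopping study drug for lack of effect, with a qualifier placing this ahead of the Week 8 evaluations.

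A failure has not achieved the dichotomous endpoints, "and for continuous end points, their last values will be carried forward for all" "visits subsequent to the time of treatment failure". The section adds: "Treatment failure rules will supersede other data handling rules".

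The continuous endpoints after Week 8 are "Change in Mayo score from baseline at Week 32" (SAP 6.19.6.1) and "Change in partial Mayo score from baseline at each visit through last available" (SAP 6.19.6.3). Both sit under Other Efficacy Analyses.

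On who is in maintenance, SAP 4 says: "All patients who complete the IP and are responders at Week 8 of the IP will enter the 24-week MP". SAP 5.2.2 defines response as a fall in Mayo score of at least 3 points and at least 30%, plus a rectal bleeding condition. It derives the full Mayo score only where there is an endoscopy. Protocol Table 1 schedules endoscopy and full Mayo at Screening, Week 8 and Week 32/ET; Week 20 has the partial score only.

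**The concern.** The two limbs of the rule treat the same patient in opposite ways. On remission and response, a maintenance patient who has a colectomy is a failure. On change in Mayo, that patient keeps the improvement held before failing. Because the failure rule takes precedence, a worse score actually observed at Week 32 would be overwritten by the better earlier one.

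The continuous analysis then describes patients partly as they were before treatment failed. Each arm's mean Week 32 improvement is overstated by an amount that grows with its number of failures, and the arm difference is distorted whenever those numbers differ.

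Nothing else in the SAP would expose this. The missing-data sensitivity analyses in SAP 6.19.5 cover the primary and key secondary endpoints, and SAP 3.2.1 does not place any Week 32 endpoint among the key secondaries. They also vary how missing data are handled, not the failure rule.

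**Working it through.** **The plan's own figure.** The only quantitative target is the sample size (Protocol 13.2, SAP 6.5): 60 per arm, 10% versus 31% remission, two-sided 0.05. With pooled rate 0.205, the null standard error is √(2 × 0.205 × 0.795/60) = 0.0737 and the alternative standard error is √((0.10 × 0.90 + 0.31 × 0.69)/60) = 0.0712. Power = Φ((0.21 − 1.96 × 0.0737)/0.0712) = 82.1%. A 20-point difference gives about 78.9%, so 21 is the smallest whole-point difference with at least 80% power. This concerns Week 8 remission; only the arm size of 60 is used below.

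**Step 1: the smallest gain a responder can carry.** Baseline Mayo runs from 6 to 12. The minimum drop is the larger of 3 and 30% of baseline rounded up. The last column is for Step 3.

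| Baseline | 30% of baseline | Minimum drop at Week 8 | Largest gain if a relapse score is carried |
|---|---|---|---|
| 6 | 1.8 | 3 | 0 |
| 7 | 2.1 | 3 | 1 |
| 8 | 2.4 | 3 | 2 |
| 9 | 2.7 | 3 | 3 |
| 10 | 3.0 | 3 | 4 |
| 11 | 3.3 | 4 | 5 |
| 12 | 3.6 | 4 | 6 |

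**Step 2: which value is carried.** With no full score scheduled between Week 8 and Week 32/ET, the last value for a maintenance failure is normally the Week 8 score. The change entered at Week 32 is then −3 or better (−4 or better for baseline 11–12).

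**Step 3: the exception.** Relapse requires partial Mayo of at least 4 and endoscopic subscore of at least 2, so a full score of at least 4 + 2 = 6. If a relapse endoscopy precedes the failure event, the carried gain is at most baseline minus 6. An early-termination endoscopy before the event would also replace the Week 8 score.

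**Step 4: partial Mayo.** The Week 4, 8 or 20 value is carried to Weeks 8, 20 or 32 in the same way, but without a 3-point floor. The endoscopy subscore can account for up to 3 points of the full drop, so the guaranteed partial drop at Week 8 is 3 − 3 = 0 (4 − 3 = 1 for baseline 11–12).

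**Step 5: full Mayo at Week 8.** The only scheduled earlier full score is baseline, so a failure before Week 8 carries a change of 0. This confirmatory analysis is barely touched.

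**Step 6: effect on one arm's mean.** Assume a failure would otherwise return to baseline (change 0). Shift = failures × carried gain / 60.

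- Gain of 3: 3 × 3/60 = 0.15; 6 × 3/60 = 0.30; 12 × 3/60 = 0.60 points.
- Gain of 6: 0.30, 0.60 and 1.20 points.

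**Step 7: effect on the arm difference.** In ITT, failures per arm = response rate × failure fraction among maintenance patients. The documents give neither, so these are illustrations with an assumed carried gain of 3 to 5 points.

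- Response 35% placebo, 55% 1 mg; failures 20% and 10%: 7.0% versus 5.5% of the arm. Bias 0.015 × 3 to 5 = 0.045–0.075 points against 1 mg.
- Same response; failures 40% and 20%: 14% versus 11%. Bias 0.09–0.15 points against 1 mg.
- Response 30% and 60%; failures 20% and 10%: 6% in each arm. No bias.
- Response 25% and 60%; same failures: 5% versus 6%. The bias favours 1 mg.
- Response 35% and 55% (21 and 33 of 60); failures 20% in both: 4.2 versus 6.6 patients. Bias 2.4/60 × 3 to 5 = 0.12–0.20 points in favour of 1 mg.

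**The case against.** **Importance.** The secondary objective for Weeks 8 and 32 names only response, remission and mucosal healing (Protocol 8.1.2, SAP 3.1.2). All are binary, and failures already count against the patient there. Change in Mayo at Week 32 is in neither document's endpoint list, and the SAP keeps it outside its testing hierarchy. This stands. The reservation is that Protocol 13.8.3 does include Week 32 change in Mayo in its confirmatory sequence, ahead of Week 32 mucosal healing.

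**Reach of the rule.** Relapse is not a listed failure, and stopping for lack of effect after Week 8 is not one on the natural reading, so the affected group is narrower than all who lose benefit. If the Week 8 qualifier limited the whole list, maintenance failures would escape the rule and only partial Mayo at Week 8, carried from Week 4, would remain. The punctuation ties the qualifier to the last item, but the wording leaves room for doubt. Nor does the SAP say outright that the last value is the one before failure; that is the natural reading of carrying it to subsequent visits.

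**Size.** A reader might take a bias computed among maintenance patients, divide it by an effect implied by the planned remission rates, and conclude that a large share of the benefit is hidden. That mixes Week 8 responders with all randomised patients. Step 7 shows the ITT bias can be small, zero or in either direction, so a bias toward no difference is not established.

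**Contrast with the protocol.** A reader might also infer that Protocol 13.11 sets the opposite rule, since there "missing values will be replaced by the least favorable observed change observed in the placebo group". That sentence governs missing values, and its SAP counterpart is the LOCF rule in SAP 6.4. The readable protocol text gives no rule for treatment failures.

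**Conclusion.** The inconsistency is real and its consequences are limited. On the natural reading of SAP 6.19, a maintenance failure with no intervening endoscopy is credited at Week 32 with at least 3 Mayo points of improvement (4 for baseline 11–12) while counting as a failure for remission and response. Change in partial Mayo at Weeks 8, 20 and 32 is affected in kind, without that minimum.

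The shift in one arm's mean is at least 0.15, 0.30 or 0.60 points for 3, 6 or 12 failures among 60. This rests on the Week 8 score being the last one before failure, on a return to baseline afterwards, and on a full-arm denominator. SAP 6.19.6.1 uses Week 32 data available at lock; if that means a smaller set of patients, each failure weighs more. The between-arm bias cannot be derived from the documents in size or sign.

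The primary endpoint and every binary endpoint are unaffected, and the Week 8 change in full Mayo nearly so. This is an improvement to consider, not a threat to the SAP's confirmatory conclusions.

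**What to change.** In SAP 6.19, replace the continuous limb with: *for continuous endpoints, at every visit after treatment failure the score is set to the worse of the baseline value and the value observed at that visit*. Where no score is observed, the baseline value stands. Apply this to change in full and partial Mayo at all induction and maintenance visits.

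In the same section, state which failure types the Week 8 qualifier limits. Keep the present carry-forward as a sensitivity analysis.

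The cost is one or two sentences and minor programming, with no new data. Mean changes will look less favourable and the spread of scores will rise slightly. Worse-of-baseline-or-observed is one defensible choice among several; its merit is that it agrees with the SAP's own binary rule. It does not alter the handling of relapse, or of stopping for lack of effect after Week 8, where these are not listed failures.
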